## 9.5 Analyses of the Other Endpoints

- 1) Serum Influenza Antibody Titer
  - Serum antibody titers measured on Day 1 and Day 22 will be categorized, and the frequency of each category and the corresponding percentage will be summarized by influenza virus subtype based on RT-PCR and treatment group.
  - The ratio of value at Day 22 to that at Day 1 will be categorized, and the frequency of each category and the corresponding percentage will be tabulated by influenza virus subtype based on RT-PCR and treatment group.
    - If serum antibody titer will be observed  $< 10$  and  $> 1280$ , the ratio of value at Day 22 to that at Day 1 will be calculated using 10 and 1280, respectively.
  - The categorized serum antibody titers at Day 1 and at Day 22 will be cross-tabulated.

- The geometric mean value of the ratio of value at Day 22 to that at Day 1 will be calculated, and the Wilcoxon rank sum test will be used to compare the ratio between two groups.

If serum antibody titer will be observed  $< 40$  due to haemolytic serum sample, the observation will be handled as missing data for the above analyses.

2) Polymorphic and treatment-emergent amino acid substitutions in the PA Gene of Evaluable Virus

The patients who have sequencing performed will be included in the following analysis.

- For the S-033188 group and the placebo group, amino acid substitutions data at the Day 1 and at the last RT-PCR positive time point will be cross-tabulated by each amino acid position in PA, influenza virus type and subtype of sequence sample and treatment group, in consiration of reference sequence.

3) Drug Susceptibility of Evaluable Virus

- The summary statistics for  $EC_{50}$  and  $IC_{50}$  at baseline will be presented by influenza virus type and subtype based on RT-PCR and treatment group.
- The summary statistics for the ratio of  $EC_{50}$  at baseline relative to  $EC_{50}$  for reference stain and the ratio of  $IC_{50}$  at baseline relative to  $IC_{50}$  for reference stain will be presented by influenza virus type and subtype based on RT-PCR and treatment group. For the patients infected with influenza A virus (A/H1N1pdm or A/H3),  $EC_{50}$  of reference strain A/Victoria/361/2011 and  $IC_{50}$  of reference strain A/Puerto/Rico/8/34 will be used. For the patients infected with influenza B virus,  $EC_{50}$  of reference stain B/Wisconsin/1/2010 and  $IC_{50}$  of reference strain B/Lee/40 will be used.

4) Change in EQ-5D-5L and EQ VAS

- The summary statistics for change in the index value and change in VAS score will be presented by treatment group at each scheduled time point.

5) Work Productivity Questionnaire

- The summary statistics for the percentage of absenteeism due to influenza illness and the percentage of work productivity loss due to influenza illness will be presented by treatment group.
- For Question 4 in Work Productivity (WP) Questionnaire, the summary statistics for the number of days required for personal assistance will be presented by treatment group. One day is equal to 24-hours.

6) Intrahousehold infection rate

Let  $K$  be the total number of patients included in this analysis,  $y_k$  be the number of  $k^{\text{th}}$  patient's household members infected between Day 1 and Day 15, and  $n_k$  be the number of  $k^{\text{th}}$  patient's household members uninfected by Day 1 ( $k = 1, \dots, K$ ). Under the assumption that  $y_k$  is distributed according to Poisson distribution with mean  $\mu_k$ , the following Poisson regression model will be applied;

$$\log(\mu_k) = \log(n_k) + \beta_0 + \beta_1 x_k$$

In the model,  $x_k$  is a group indicator variable for the  $k^{\text{th}}$  patient, i.e.,  $x_k = 1$  for the S-033188 group,  $x_k = 0$  for the control group (the placebo group or the oseltamivir group). The  $\beta_0$  is an intercept parameter,  $\beta_1$  is a regression parameter. Intrahousehold infection rates for the S-033188 group and the control group are given by  $\exp(\beta_0 + \beta_1)$  and  $\exp(\beta_0)$ , respectively. Estimate and 95% CI of intrahousehold infection rate of each treatment group and comparison between two treatment groups will be carried out using the following SAS code. In addition, a risk ratio of the S-033188 group to the control group and the corresponding 95% CI will be estimated by the above Poisson regression model.

```
Data analysisdata;  
  set analysisdata;  
  lnum=log(NUM);  
run;
```

[Comparison between the S-033188 group and the placebo group]

```
proc genmod data = analysisdata;  
  class TRTP;  
  model RES = TRTP / dist = poisson link = log offset = lnum;  
  lsmeans TRTP / cl exp;  
  estimate "S-033188 vs Placebo" TRTP 1 -1 / exp;  
run;
```

- NUM: Number of household members uninfected by Day 1
- TRTP: Treatment group (1:S-033188, 2:Placebo)
- RES: Number of household members infected between Day 1 and Day 15

[Comparison between the S-033188 group and the Oseltamivir group]

```
proc genmod data = analysisdata;  
  class TRTP;  
  model RES = TRTP / dist = poisson link = log offset = lnum;  
  lsmeans TRTP / cl exp;  
  estimate "S-033188 vs Oseltamivir" TRTP 1 -1 / exp;  
run;
```

- NUM: Number of household members uninfected by Day 1
- TRTP: Treatment group (1:S-033188, 3:Oseltamivir)
- RES: Number of household members infected between Day 1 and Day 15

The similar Poisson regression model will be applied using the number of household members  $y_k$  infected during each of the following time periods as a response variable;

- From Day1 to Day 3
- From Day 1 to Day 4
- From Day1 to Day 6
- From Day 1 to Day 11

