9.13 Other Analysis

9.13.1 Serum Influenza Antibody Titer

Serum antibody titers measured at Visit 1 (Day 1) and Visit 7 (Day 22) will be categorized, and the frequency of each category will be tabulated by treatment group. The ratio of value at Visit 7 to that at Visit 1 will be categorized, and the frequency of each category will be tabulated by treatment group. For the ratio (Visit 7/Visit 1), the geometric mean value will also be calculated, and S-033188 group will be compared with the placebo group regarding the geometric mean ratio, using the Wilcoxon rank sum test.

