### 9.3 Other Endpoints

1) Serum influenza antibody titer

This endpoint is defined as the ratio of value on Day 22 to that on Day 1.

2) Polymorphic and treatment-emergent amino acid substitutions in the PA gene of evaluable virus

This endpoints is defined as follows:

- The percentage of samples which have polymorphic amino acid substitutions on Day 1 compared to the reference sequence
- The percentage of samples which have treatment-emergent amino acid substitutions between Day 1 and the time point when last positive RT-PCR is obtained

For treatment-emergent amino acid substitutions in the PA gene, sequencing data obtained at the baseline (Day 1) and last RT-PCR positive timepoint will be compared for treatment-emergent amino acid substitutions in the PA gene in the S-033188 group and placebo group, respectively.

For polymorphic amino acid substitutions in the PA gene, sequencing data obtained at the baseline (Day 1) will be compared to that of the reference sequence in the S-033188 group and the placebo group, respectively.

The patients who have sequencing performed will be included in this analysis.

3) Drug susceptibility in patients with evaluable virus (unit: EC50 nM, IC50 nM)

This endpoints is defined as follows:

- EC50 for S-033447 at baseline
- IC50 for oseltamivir at baseline
- The ratio of EC50 for S-033447 relative to EC50 for reference stain
- The ratio of IC50 for oseltamivir relative to IC50 for reference stain

If the EC50 is less than the lower limit, the EC50 will be imputed the lower limit

value (0.03 nM). If the EC50 is greater than upper limit, the EC50 will be imputed as the value of upper limit (1000 nM).

If the IC50 is less than the detection limit, the IC50 will be imputed detection limit value (0.01 nM). If the IC50 is greater than upper limit, the IC50 will be imputed as the value of upper limit (10000 nM).

The patients with a detected value at baseline will be included in this analysis. However, the patients infected with multiple virus types will be excluded from this analysis.

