**Table 8 Category of Variable**

Variable	Category
Age	12-19 years, 20-29 years, 30-39 years, 40-49 years, 50-59 years, 60-64 years
Body weight	<80 kg, ≥80 kg
Timing of meal before and after dosing	<2 hours, 2 to 4 hours, > 4 hours
Time of onset of influenza symptoms	0-12 hours, 12-24 hours, 24-36 hours, 36-48 hours
Influenza virus subtype based on RIDT	A, B, A and B, Negative, Unknown
Influenza virus subtype based on RT-PCR	A/H1N1pdm: A/H1N1pdm A/H3: A/H3 B:B Mixed infection: A/H1N1pdm and B, A/H3 and B, A/Unknown and B, A/ND and B, A/H1N1pdm and A/H3 and B, A/H1N1pdm and A/H3 Other: A/Unknown, A/ND, Unknown Negative:
	The above virus subtype classification is derived from the following specification:
	- A/H1N1pdm: H1_2009
	- A/H3: H3
	- A/H1N1pdm and A/H3: H1_2009/H3
	- A/ND: ND
	- A/Unknown: UNKNOWN
Virus subtype classification used for subgroup analysis	A/H1N1pdm, A/H3, B
Serum influenza antibody titer (Day 1, Day 22)	<10, ≥10 to <20, ≥20 to < 40, ≥40 to < 80, ≥80 to <160, ≥160
Serum influenza antibody titer (Ratio of Day 22 relative to Day 1)	<4, ≥4 to <8, ≥8 to <16, ≥16 to <32, ≥32 to <64, ≥64 to <128, ≥128 to <256, ≥256
Composite symptoms score at baseline	≤11, ≥12
Treatment compliance rate	<80, ≥80
Acetaminophen use	0, 1-2, 3-4, ≥5
Time of onset of AE	Week 1 (≥1 day to <8 days), Week 2 (≥8 days to <15 days), Week ≥3 (≥15 days)
Urine protein	-, 1+, 2+, 3+, Unknown
Urine glucose	-, 1+, 2+, 3+, 4+, Unknown
Urobilinogen	-, 1+, 2+, 3+, 4+, Unknown
Urine occult blood	-, 1+, 2+, 3+, 4+, Unknown

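### The antibody substitution rule caps the Day 22/Day 1 ratio at 128, so Table 8's top class cannot be filled, and it scores a rise from below 10 to 10 as no change

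*SAP*

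**What the plan says.** SAP 9.3 item 1 defines the antibody endpoint: "This endpoint is defined as the ratio of value on Day 22 to that on Day 1". SAP 9.5 item 1 then handles readings outside the assay range. For titers below 10 or above 1280, "the ratio of value at Day 22 to that at Day 1 will be calculated using 10 and 1280, respectively".

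The ratio is used in three ways in SAP 9.5 item 1. It is tabulated by class, summarised as a geometric mean, and tested: "the Wilcoxon rank sum test will be used to compare the ratio between two groups". Table 8 sets the ratio classes, which start at below 4 and end with "≥64 to <128, ≥128 to <256, ≥256". For the titers themselves, Table 8 keeps below 10 as a class separate from 10 to below 20.

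A further display does not use the ratio: "The categorized serum antibody titers at Day 1 and at Day 22 will be cross-tabulated".

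Protocol 9.13.1 plans the same analysis ("The ratio of value at Visit 7 to that at Visit 1 will be categorized") but gives no substitute for titers outside the assay range.

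**The concern.** There are two problems. First, the rule in SAP 9.5 and the classes in Table 8 do not fit together: Table 8 reserves a class that the rule makes impossible to reach.

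Second, a reading below 10 is treated as if it were 10. Table 8 regards these as different titer states, yet a patient who moves from one to the other gets a ratio of 1, the same as a patient whose titer did not move. For patients who start without measurable antibody and then develop it, the plan reports a lower bound as though it were the value. That carries into the class table, the geometric mean and the ranks used in the test. At stake is how the antibody response is described, not any confirmatory claim.

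**Working it through.** **Inputs from the SAP.** Below 10 becomes 10 and above 1280 becomes 1280 (9.5 item 1). The top ratio class is 256 or more (Table 8).

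**Inputs not in the documents (assumptions).** The value that stands for a reading below 10: 5 is used as the reference, with 7.07 and 2.5 as the range. Twofold titer steps from 10 to 1280. The share f of patients with Day 1 below 10 and Day 22 of 10 or more.

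**1. Can the top class be reached?** Both numerator and denominator lie between 10 and 1280, so the largest ratio is 1280/10 = 128. This does not depend on the titer steps. The class of 256 or more is therefore unreachable, and the class from 128 to below 256 can hold only 128. With the upper limit kept at 1280, a ratio of 256 needs a denominator of 1280/256 = 5 or less.

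| Substitute for below 10 | Largest ratio | Class of 256 or more reachable? |
|---|---|---|
| 10 (SAP) | 128 | no |
| 7.07 | 181 | no |
| 5 | 256 | yes, at exactly 256 |
| 2.5 | 512 | yes |

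**2. Direction for patients who start below 10.** With Day 22 of 10 or more, any denominator below 10 gives a larger ratio than the SAP's. The SAP ratio is too small by the factor 10/substitute: 10/7.07 = 1.41, 10/5 = 2, 10/2.5 = 4.

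**3. Effect on classes, against 5 (Day 1 below 10).**

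| Day 22 | SAP ratio (class) | Ratio with 5 (class) |
|---|---|---|
| below 10 | 1 (<4) | 1 (<4) |
| 10 | 1 (<4) | 2 (<4) |
| 20 | 2 (<4) | 4 (4 to <8) |
| 40 | 4 (4 to <8) | 8 (8 to <16) |
| 160 | 16 (16 to <32) | 32 (32 to <64) |
| 640 | 64 (64 to <128) | 128 (128 to <256) |
| 1280 or above | 128 (128 to <256) | 256 (256 or more) |

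The class changes only from Day 22 = 20 upward.

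**4. Effect on the geometric mean ratio, against 5.** Doubling the ratio in a share f of patients multiplies the geometric mean by 2^f, so the SAP figure is lower by 1 − 2^(−f):

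- f = 0.2: 1 − 2^(−0.2) = 13%
- f = 0.4: 1 − 2^(−0.4) = 24%
- f = 0.6: 1 − 2^(−0.6) = 34%

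Varying the substitute at f = 0.4: with 7.07, 1 − 1.41^(−0.4) = 13%; with 2.5, 1 − 4^(−0.4) = 43%. These figures assume that nobody falls from 10 or more to below 10. If a share g does, the rule overstates their ratio (20 to below 10 gives 10/20 = 0.5, against 5/20 = 0.25 with 5), and the exponent becomes f − g.

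**5. Between arms, against 5.** The ratio of geometric means changes by 2 raised to the difference in f between the arms. With equal f the factor is 2^0 = 1.

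**The case against.** The strongest reply is that substituting the limit itself is this SAP's own convention. Virus titer below the limit is set to 0.7 and undetected RNA to 2.05 or 2.83 (9.2 items 3 and 4). EC50 and IC50 are set to their lower or upper limits (9.3 item 3). On this view the antibody rule is consistent, and an unused row in Table 8 changes no estimate. The cross-tabulation also keeps the class below 10, so patients who seroconvert remain visible. The endpoint lies outside the hierarchical testing in SAP 6.2, and one rule applies to every arm.

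Most of that stands. It limits the importance of the point but does not remove it. The convention does not make 10 a possible value for a reading below 10. The cross-tabulation cannot correct the geometric mean or break the ties in the rank test, and its top titer class is 160 or more, so large ratios cannot be recovered from it.

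A reader might infer more than the documents support:

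- **That responses are halved.** This is true only against 5, which appears nowhere in the documents.
- **That Table 8 shows 5 was intended.** A class of 256 or more could equally come from an uncapped 2560/10.
- **That the lower substitution alone causes the cap, or that only patients starting below 10 are affected.** The cap also needs the truncation at 1280, which itself understates ratios when Day 22 is above 1280 and Day 1 is measurable.
- **That the rule hides a blunted immune response on S-033188.** No objective or section gives this as the purpose of the test. A compressed contrast needs f to differ between arms. Shares of 50% and 30% would give 2^0.2 = 1.15, but those shares are invented for illustration.

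**Conclusion.** The point holds, as a minor one. It is certain from the SAP alone that the ratio cannot exceed 128, that Table 8's top class will stay empty, and that the ratio is a lower bound for every patient going from below 10 to 10 or more.

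The size of the shortfall is not fixed by the documents. It is a factor of 1.41 to 4 per affected patient over substitutes from 7.07 to 2.5. For the geometric mean it also depends on the unknown share f. The rank test is not biased when the arms do not differ. It may lose some sensitivity through ties, for example between patients who go from below 10 to 10 and patients with no change; this loss was not quantified. The primary and key secondary comparisons are not affected.

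**What to change.** Before unblinding, reconcile SAP 9.5 item 1 with Table 8. In the ratio, replace titers below 10 by 5, one twofold step below the limit, and label this as an assumption. The maximum then becomes 1280/5 = 256 and Table 8 needs no edit, although its top class will hold only that one value. Keep the rule for titers above 1280, and add a note that ratios with a Day 22 titer above 1280 remain lower bounds when Day 1 is within range.

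The cost is one number and one sentence in the SAP. No new data are needed, and there is no conflict with Protocol 9.13.1, which names no substitute. The downsides are small: the value below the limit is still assumed, and the rule would depart from the limit-value convention used for the other assays.

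If the sponsor prefers to keep 10, Table 8 should end at 128 or more and ratios with Day 1 below 10 and Day 22 of 10 or more should be labelled as lower bounds. That repairs the table but leaves the rise from below 10 to 10 scored as no change.

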## 6.4 Handling of Missing Data

Missing data will not be imputed.

- Patients who do not experience alleviation of symptoms will be censored at the last observation time point, except in the case of sensitive analysis for primary analysis.
  - If all symptoms were missing after baseline, time to alleviation of symptoms, time to alleviation of symptoms excluded cough, time to alleviation of the 4 systemic symptoms, time to alleviation of the 3 respiratory symptoms and time to alleviation of individual symptoms will be handled as missing.
- For the sensitive analysis for primary endpoint, the patients who do not experience alleviation of symptoms will be treated as follows.
  - If patients who discontinue from the study and still have influenza symptoms, time to alleviation of symptoms will be censored as 14 days.
  - In consideration of treatment duration of the oseltamivir group.
    - If patients who discontinue until Day 5 and still have influenza, time to alleviation of symptoms will be censored at the last observation time point.
    - If patients who discontinue after Day 5 and still have influenza, time to alleviation of symptoms will be censored as 14 days.
  - In consideration of the reason of the discontinuation.
    - If patients discontinue due to AE or lack of efficacy, time to alleviation of symptoms will be censored as 14 days.
    - If patients discontinue due to other reason, time to alleviation of symptoms of the patients will be censored at the last observation time point.

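### SAP 9.5 1) sets haemolysed serum titers to missing only when they read below 40, so read literally the missingness depends on the titer; the effect on an other endpoint is small

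*SAP*

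**What the plan says.** Serum antibody titer is an other endpoint. SAP 9.3 1) states: "This endpoint is defined as the ratio of value on Day 22 to that on Day 1". SAP 9.5 1) tabulates Day 1 and Day 22 titers by class, tabulates the ratio by class, cross-tabulates the two days and gives the geometric mean ratio. For inference, "the Wilcoxon rank sum test will be used to compare the ratio between two groups".

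Two rules cover values that cannot be used as reported:

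- **Ordinary assay limits.** Where a titer is below 10 or above 1280, the ratio "will be calculated using 10 and 1280, respectively". These values stay in.
- **Haemolysis.** A titer observed below 40 because of haemolysis is not substituted: "due to haemolytic serum sample, the observation will be handled as missing data for the above analyses". The sentence closes the subsection, so it reaches every antibody output listed before it.

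SAP 6.4 adds "Missing data will not be imputed", so a titer set to missing also removes that patient's Day 22/Day 1 ratio. Table 8 gives the titer classes as "<10, ≥10 to <20, ≥20 to < 40, ≥40 to < 80, ≥80 to <160, ≥160"; three of the six lie wholly below 40.

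Protocol 9.13.1 says "Serum antibody titers measured at Visit 1 (Day 1) and Visit 7 (Day 22) will be categorized" and has no haemolysis rule. SAP section 14 does not mention one. Neither document gives the haemolysis rate, a reason for the value 40, a count of affected samples or a sensitivity analysis for the rule.

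**The concern.** Haemolysis is a property of the sample, so its handling should not depend on the result obtained. As written, deletion happens on the low side only. On Day 22, a haemolysed sample is lost exactly when the patient stayed below 40. On Day 1, it is lost when the baseline was below 40. Among haemolysed samples, three of the six titer classes are always emptied and three are kept.

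The phrase about titers below 40 can be read in two ways, and neither justifies one-sided deletion:

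- If haemolysis raises the reporting limit to 40, the result is left-censored. Deleting it discards the information that the titer was low.
- If haemolysis makes readings unreliable, readings of 40 or more from such samples are also in doubt.

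At stake are the class tables, the per-arm geometric mean ratio and, to a lesser degree, the estimated difference in antibody response between arms.

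**Working it through.** The plan states no figure for this rule, so there is nothing to reproduce. The check has three parts. All haemolysis rates and titer distributions below are assumptions.

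**1. Share of titers at or above 40.** Let p be the true share at or above 40, and h the haemolysis rate, independent of titer. The rule removes a fraction h of the titers below 40, so

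observed share = p / (1 − h(1 − p)).

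Example: for p = 0.5 and h = 0.10, 0.5 / (1 − 0.10 × 0.5) = 0.5 / 0.95 = 52.6%, an excess of 2.6 points.

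| p | h = 1% | h = 5% | h = 10% | h = 20% |
|---|---|---|---|---|
| 0.2 | +0.16 | +0.83 | +1.74 | +3.81 |
| 0.5 | +0.25 | +1.28 | +2.63 | +5.56 |
| 0.8 | +0.16 | +0.81 | +1.63 | +3.33 |

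(Excess in percentage points.)

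**2. Per-arm geometric mean ratio.** Simulation of 1,000,000 pairs per setting. Assumed: twofold dilutions, the SAP limits 10 and 1280, Day 1 geometric mean 20, log2 SD 1.7 on Day 1 and 1.7 for the change, an underlying 4-fold rise, and haemolysis at each visit independent of titer and arm.

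| h | no deletion | SAP rule | all haemolysed dropped |
|---|---|---|---|
| 1% | 3.26 | 3.28 | 3.26 |
| 5% | 3.27 | 3.33 | 3.26 |
| 10% | 3.26 | 3.40 | 3.27 |
| 20% | 3.26 | 3.54 | 3.27 |

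The no-deletion value is below 4 because of the limits 10 and 1280. At 10% haemolysis the share with a ratio of at least 4 moves from 52.1% to 54.1%. Almost all of the shift comes from Day 22: with 10% haemolysis at Day 22 only, 3.27 becomes 3.39; at Day 1 only, 3.26 becomes 3.28. With Day 1 geometric means of 15 or 40 and rises of 4- or 8-fold, the shift has the same direction. At 10% it runs from 3.05 to 3.19 (Day 1 mean 15, 4-fold) at the larger end and from 6.40 to 6.49 (Day 1 mean 40, 8-fold) at the smaller.

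**3. Contrast between arms.** Two-arm simulation of 2,000,000 pairs per arm. Assumed: an 8-fold rise on placebo against 5-fold on S-033188, Day 1 geometric mean 20, log2 SD 1.7 at each visit, and a Day 1 to Day 22 correlation of 0.5. The figure is the S-033188 geometric mean ratio divided by the placebo one.

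| h | no deletion | SAP rule | relative change |
|---|---|---|---|
| 1% | 0.637 | 0.637 | none visible |
| 5% | 0.637 | 0.639 | 0.639/0.637 = +0.3% |
| 10% | 0.637 | 0.642 | 0.642/0.637 = +0.8% |
| 20% | 0.638 | 0.648 | 0.648/0.638 = +1.6% |

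A wider gap (4-fold against 8-fold, correlation 0.6) gave 0.517 without deletion, 0.521 at 10% (+0.8%) and 0.527 at 20% (+1.9%). Both arms shift upward, so most of the bias cancels.

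**The case against.** The strongest reply has four parts.

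- **Retention of readings of 40 or more is inferred from silence.** The SAP never says that such haemolysed samples are kept. Sample handling is left to a separate document (Protocol 7.6.4.5). If no haemolysed sample can give a result of 40 or more, nothing is selected among the haemolysed results. This stands as a condition on the point. The documents do not say that such results cannot occur, and as the text reads they would enter as ordinary values.
- **The rule may have a sensible purpose.** A result known only to be below 40 fits none of the three lower classes in Table 8 and gives no exact ratio. Dropping it as unquantifiable is understandable. That explains the rule but does not remove the selection. The same subsection keeps results below 10 by substitution, without saying why the two low limits are treated differently.
- **The size is unknown and may be nil in practice.** This stands. Near 1% haemolysis no estimate moves noticeably.
- **The simulations take titers as true and haemolysis as independent of titer.** This also stands. If haemolysis falsely lowers readings, they do not describe the situation.

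A reader might infer that the rule conceals a blunted antibody response on S-033188 or invalidates the group comparison. The documents do not support that. They contain nothing linking haemolysis to arm. If the two are unrelated, the rule acts alike in both arms when treatment has no effect, and the Wilcoxon test keeps its type I error. When responses do differ, the attenuation is slight.

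**Conclusion.** Wrong as written, low severity. The SAP conditions deletion of a haemolysed result on the result's own value, and it plans no count or sensitivity analysis that would show whether this matters. The clearest effect is on the class tables: an excess of roughly 1 to 3 points in the share at or above 40 for haemolysis of 5 to 10%, about 3 to 5.6 points at 20%, and a negligible amount near 1%. Under the main simulated setting the per-arm geometric mean ratio rises by about 2%, 4% and 9% at 5%, 10% and 20% (3.33/3.27, 3.40/3.26, 3.54/3.26). The contrast between arms is attenuated by under 1% up to 10% haemolysis and by about 1.5 to 2% at 20%.

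These sizes rest on assumed haemolysis rates and titer distributions, on independence of haemolysis from titer and arm, and on haemolysed readings of 40 or more occurring and being kept. The direction for the class shares follows from the rule. The direction for the ratio depends on which visit is affected and on how the rise relates to the Day 1 titer.

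**What to change.** Make the haemolysis rule in SAP 9.5 1) independent of the value, by one of two routes:

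1. Set every titer from a haemolysed sample to missing at that visit, whatever it reads. In the simulation this restored the no-deletion ratio.
2. If readings of 40 or more are considered valid, or if the laboratory flags haemolysis only on results below 40, keep those results as a separate class, < 40 (haemolysed), in the titer tables. As a sensitivity check, bound the ratio by substituting first 10 and then 40. A rank test for interval-censored data is more than this endpoint needs.

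Under either route, report the number of haemolysed samples by arm and visit. A rate near 1% would settle the matter.

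The cost is one amended sentence and one small count table; route 2 also needs the extra class and the bounding run. Route 1 loses more pairs, including any valid readings of 40 or more. With haemolysis rate h at each visit, it drops 1 − (1 − h)² of pairs: 2.0% at h = 1%, 9.8% at 5% and 19.0% at 10%. The present rule loses 1.1%, 5.2% and 10.3% in the main simulated setting. At low rates this is a few pairs; at 10% route 2 becomes the more attractive choice.
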